Vaccine Effectiveness and Seroconversion to 23
Valent Pneumococcal Polysaccharide
Vaccination in Children With Type 1 Diabetes

NCT04481243

4/22/2022

General Study Information

Co-Principal Investigator:

██████████ MD, MS

[name]

Investigators

██████████, Ph.D.

██████████, MD

Study Title: Vaccine effectiveness and seroconversion to 23 Valent Pneumococcal Polysaccharide Vaccination in Children with Type 1 Diabetes

Protocol version number and date: Version 4, 4/22/2022

Research Question and Aims

Hypothesis: Children with Type 1 Diabetes have reduced immunological response to 23 valent polysaccharide pneumococcal vaccination (PPSV23) as assessed by global IgG levels.

Aims, purpose, or objectives:

Specific Aim 1: To determine if children with type 1 diabetes have adequate immune response to PPSV23 vaccination and to assess factors affecting immune response.

Hypothesis 1: Children with type 1 diabetes (T1DM) will have a suboptimal immunological response to PPSV23 as assessed by global IgG assay. Lower age of the patient, longer duration of diabetes and poor glycemic control will be associated with impaired immunogenic response to the PPSV23.

Specific Aim 2: To assess if patients with T1DM have waning of immune response to PPSV23 six months following vaccination and associated factors that may be associated with the vaccine response.

Hypothesis 2: T1DM children will have higher waning of immunity as compared to general population without T1DM. Lower age of the patient, longer duration of diabetes and poor glycemic control will be associated with impaired immunogenic response to the PPSV23.

Background:

Diabetics are at risk for invasive pneumococcal infections and are more likely to have severe outcomes with infection compared to the general population.¹⁻³ Half of all school-age children with T1DM are colonized with *Streptococcus pneumoniae*, underscoring the need for pneumococcal vaccination.⁴ While the CDC recommends all children > 2 years with type 1 diabetes receive PPSV23 to prevent invasive pneumococcal disease, literature suggests lack of compliance and missed opportunities for PPSV23 vaccination in diabetic children.^{5,6} Furthermore, it is unknown if children with T1DM mount sufficient immunological response to PPSV23 vaccination.

PPSV23 immunological response relies upon the adaptive immune system including adequate T-cell activation by antigen presenting cells, T-cell proliferation, subsequent B-cells stimulation, and antibody production. While definitive data on the degree of global adaptive immune impairment in diabetics remains unclear, there are likely some T-cell interactions with antigen presenting cells that explain the decreased antibody response to vaccination. Adult studies indicate decreased antibody response to T-cell dependent antigens via altered antigen-presenting T-cell interactions.⁷ Others describe functional immune impairments including abnormal CD4, CD8, and CD8 Treg proliferation as well as abnormalities in the antigen presenting cell including monocyte derived dendritic cells having reduced CD54 adhesion molecules and increased inhibitory cytokines (IL-10) in type 1 diabetics.^{8,9} Mechanisms of poorer T-cell proliferation may be due to reduced antigen-induced interferon- γ and interleukin-13 release in type 1 diabetics compared to type 2 diabetics.⁷ Limited data in children with type 1 diabetes also suggest reduced antibody response to T-cell dependent antigens such as the PPSV23.¹⁰

New techniques are available to assess antibody response to T-cell dependent antigens. Total IgG levels have traditionally been used to help assess serological response to vaccination though four separate IgG subclasses characterized by distinct immune properties exist. Assessing global IgG studies which include all subtypes may better inform clinicians of immune response. We hypothesize that serological response to PPSV23 as assessed by global IgG, IgM, and IgA response will be altered in T1DM. Better understanding the immune response to PPSV23 may lead to better timing of vaccination in relation to diabetes diagnosis, optimize diabetes care to prevent sustained and uncontrolled hyperglycemia around the time of infection, and perhaps even inform the need for further booster PPSV23 vaccinations. Optimizing PPSV23 vaccination may decrease invasive pneumococcal infections and related morbidity in young patients with T1DM.

Study Design and Methods

Methods: *Describe in lay terms, completely detailing the research activities that will be conducted by Mayo Clinic staff under this protocol.*

We aim to identify children with T1DM 3-18 years of age who have not received pneumococcal polysaccharide vaccination (Pneumovax 23). The diagnosis of T1DM will be confirmed clinically based upon a hemoglobin A1C > 6.5% and history consistent with T1DM. Children with other diseases known to significantly compromise immunity and vaccine response will be excluded. Target accrual will be 100 children.

Seroconversion assessment: Vaccine response as assessed by Global IgG will be drawn 6 months after immunization (+/- 4 months). Blood draws will be aligned when possible with the participant's quarterly clinical hemoglobin A1C checks, to minimize additional blood draws. Key clinical information will be abstracted including hemoglobin A1C history, years of diabetes, glucose variability, diabetes technology use, and anthropometric data.

Subject Information

Target accrual is the proposed total number of subjects to be included in this study at Mayo Clinic. A "Subject" may include medical records, images, or specimens generated at Mayo Clinic and/or received from external sources.

Target accrual: 100

Subject population (children, adults, groups): children ages 3-18 years

Inclusion Criteria:

-Clinical diagnosis of Type 1 diabetes

Exclusion Criteria:

- Newly diagnosed with Type 1 diabetes within the past month of study date
- Contraindications to receiving 23 valent pneumococcal vaccines
- Other conditions associated with compromised immunity and vaccine response
- Primary or Secondary Immune deficiency
- Previous receipt of PPSV-23 vaccination

Biospecimens

Collection of blood samples. When multiple groups are involved copy and paste the appropriate section below for example repeat section b when drawing blood from children and adults with cancer.

a. **From healthy, non-pregnant, adult subjects who weigh at least 110 pounds.** For a minimal risk application, the amount of blood drawn from these subjects may not exceed 550ml in an 8 week period and collection may not occur more frequently than 2 times per week.

Volume per blood draw: ____ up to 6 ____ ml

Frequency of blood draw (e.g. single draw, time(s) per week, per year, etc.) ____ twice: baseline 4-6 months post immunization _____

b. **From other adults and children considering age, weight, and health of subject.** For a minimal risk application, the amount of blood drawn from these subjects may not exceed the lesser of 50 ml or 3 ml per kg in an 8 week period, and collection may not occur more frequently than 2 times per week.

Volume per blood draw: ____ up to 6 ____ ml

Frequency of blood draw (e.g. single draw, time(s) per week, per year, etc.) ____ baseline 4-6 months post immunization _____

Prospective collection of biological specimens other than blood: _____

Review of medical records, images, specimens

Check all that apply (data includes medical records, images, specimens).

Only data that exists before the IRB submission date will be collected.

Date Range for Specimens and/or Review of Medical Records:

Examples: 01/01/1999 through 12/31/2015, or all records through mm/dd/yyyy.

Note: The Date Range must include the period for collection of baseline data, as well as follow-up data, if applicable.

X The study involves data that exist at the time of IRB submission **and** data that will be generated after IRB submission. Include this activity in the Methods section.

Examples

- The study plans to conduct a retrospective chart review and ask subjects to complete a questionnaire.
- The study plans to include subjects previously diagnosed with a specific disease and add newly diagnosed subjects in the future.

The study will use data that have been collected under another IRB protocol. Include in the Methods section and enter the IRB number from which the research material will be obtained. *When appropriate, note when subjects have provided consent for future use of their data and/or specimens as described in this protocol.*

Enter one IRB number per line, add more lines as needed

Data Specimens Data & Specimens _____

Data Specimens Data & Specimens _____

Data Specimens Data & Specimens _____

Data Analysis

Power analyses may not be appropriate if this is a feasibility or pilot study, but end-point analysis plans are always appropriate even if only exploratory. Provide all information requested below, or provide justification if not including all of the information.

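### The plan as written cannot show whether the PPSV23 response in children with T1DM is reduced, inadequate or faster-waning: it has no comparator, no response definition and, on the natural reading, one post-vaccination draw

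*Combined protocol and SAP*

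**What the plan says.** **Claims (Research Question and Aims).** The main hypothesis is that "Children with Type 1 Diabetes have reduced immunological response to 23 valent polysaccharide pneumococcal vaccination (PPSV23) as assessed by global IgG levels". Aim 1 is "To determine if children with type 1 diabetes have adequate immune response to PPSV23 vaccination", and Hypothesis 1 states that these children "will have a suboptimal immunological response to PPSV23 as assessed by global IgG assay". Aim 2 is "To assess if patients with T1DM have waning of immune response to PPSV23 six months following vaccination", and Hypothesis 2 states that "T1DM children will have higher waning of immunity as compared to general population without T1DM". Both aims also ask which factors (age, diabetes duration, glycemic control) go with a weaker response. The Background gives the rationale: "it is unknown if children with T1DM mount sufficient immunological response to PPSV23 vaccination".

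**Population (Subject Information).** The one inclusion criterion is "Clinical diagnosis of Type 1 diabetes". Target accrual is 100. No group without T1DM is described.

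**Sampling.** Methods gives one post-vaccination time point, 6 months with 4 months either way: "Seroconversion assessment: Vaccine response as assessed by Global IgG will be drawn 6 months after immunization (+/- 4 months". It mentions no baseline draw. The Biospecimens fields list a baseline and a 4-6 month draw. The count of two appears only in section a (healthy adults). Section b, which covers children, lists the same draws without a count or punctuation.

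**Analysis (Data Analysis Plan and Endpoints).** Clinical data are described, and Global IgG is checked for normality and transformed or handled nonparametrically if needed. Linear models with two-way interactions relate serological response to HbA1c, diabetes duration, glucose variability, BMI, age at vaccination and similar variables, with two-sided alpha 0.05. The primary endpoint is serological response by Global IgG, with no numerical definition.

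**The concern.** A reduced response is reduced relative to something. An adequate or suboptimal one is judged against a threshold. Waning is a fall from an earlier, higher value. The plan supplies none of the three reference points, so followed exactly it would deliver a distribution of Global IgG and associations among children who all have T1DM. Such associations can suggest which of these children respond less well. They cannot show that T1DM itself lowers the response.

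At stake is the question that the Background gives as the reason for the study. With no response definition on paper, adequacy could be defined once the results are known. Because the same post-vaccination sample serves both aims, a low value could reflect a poor initial response or decay after a good one.

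**Working it through.** **1. No stated figure to reproduce.** The target of 100 comes with no effect size, SD, power, precision target or dropout rate. The check therefore matches each claim to the data and analysis that it needs.

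| Claim | What it needs | What the plan has |
|---|---|---|
| Reduced response (main hypothesis) | A non-T1DM group or a designated reference | Neither |
| Adequate / suboptimal (Aim 1, Hypothesis 1) | A response definition and a standard to judge it by | Neither; no pre/post contrast is written |
| Waning (Aim 2) | At least two post-vaccination values per child | One, on the natural reading |
| More waning than without T1DM (Hypothesis 2) | The above, plus non-T1DM data | Neither |
| Associated factors (both aims, secondary endpoint) | Within-T1DM models | Planned |

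The first four rows come down to three gaps: no comparator, no response definition, and no earlier post-vaccination value.

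**2. What the missing cut-off can do (assumed distribution).** Suppose that fold rise is lognormal with geometric mean 3 and log-SD 0.8. The responder share at cut-off c is 1 − Φ[(ln c − ln 3)/0.8].
- c = 2: 1 − Φ(−0.507) = 69%
- c = 3: 1 − Φ(0) = 50%
- c = 4: 1 − Φ(0.360) = 36%

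Over geometric means 2 to 4 and log-SDs 0.6 to 1.0, the share for these cut-offs runs from 12% to 88%.

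**3. Why one post-vaccination value cannot show waning (assumed peak at 1 month, exponential decay).** The net ratio to baseline at month 6 is peak × 2^(−(6 − 1)/half-life).
- Peak 2-fold, no decay: 2.0
- Peak 4-fold, half-life 5 months: 4 × 2^(−1) = 2.0
- Peak 8-fold, half-life 2.5 months: 8 × 2^(−2) = 2.0

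Three different histories give the same observation.

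**4. The indirect route.** The Methods window runs from 6 − 4 = 2 to 6 + 4 = 10 months, so children would differ in time since vaccination. Regressing Global IgG on that time would give a between-child slope, not a within-child decline, and would still have no non-T1DM comparator. Time since vaccination is not among the named model variables, although that list is open-ended.

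**5. What single-arm estimation could deliver.** With 100 evaluable children (no attrition assumed), exact 95% intervals for a responder proportion are 40-60% at an observed 50%, 60-79% at 70%, and 82-95% at 90%. That is a usable estimate once a cut-off exists.

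**The case against.** The strongest reply is that the plan holds more than its wording shows. A baseline draw is listed and the analysis refers to response parameters, so a change from baseline was probably intended. The linear models answer real parts of both aims. The Background cites earlier work, including a case-control study in children with T1DM, and the protocol form itself allows for exploratory work.

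The credit for the models stands in full, and the intended change score is plausible. But no such analysis is written, and a rise from baseline alone shows neither adequacy nor a deficit against other children. The cited studies are background; none is designated as a reference. The protocol does not call itself a pilot, and its form asks for an endpoint analysis plan even for exploratory work.

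Some stronger readings are tempting but not supported:
- *Adequacy will be defined after the data.* The documents show only that no definition is written. It can still be fixed before assay results are seen.
- *The two-draw schedule is settled.* It is inferred from an unpunctuated children's field and from a count that appears only in the adult field.
- *Words lost from the text might have held a definition.* The Global IgG phrase in the Data Analysis Plan has an unclosed bracket and the primary endpoint ends on a comma, so words may be missing. Nothing suggests that a cut-off or comparator was among them.

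**Conclusion.** The point holds and should be fixed. As written, the plan cannot support or refute the main hypothesis, the adequacy part of Aim 1 and Hypothesis 1, or the waning part of Aim 2 and Hypothesis 2. The missing comparator and response definition follow directly from the text. The waning gap rests on reading the schedule as a baseline plus one post-vaccination draw. Even if a further draw were intended, the comparison with people without T1DM would still have no data source. The figures for cut-off and decay are illustrations under stated assumptions, and the conclusion does not depend on them.

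A reader might infer that the study can answer nothing. It can: the associated-factors questions and the secondary endpoint have a planned analysis. A reader might also infer that 100 children are too few to judge adequacy. The documents set no bar, so that cannot be said.

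**What to change.** 1. **Hypothesis, Aim 1, Hypothesis 1.** Restate as single-arm estimation with no conclusion relative to children without T1DM. Alternatively, prespecify a named external reference with a comparable assay and sampling time, and carry its uncertainty into the comparison.
2. **Aim 2, Hypothesis 2.** Drop the comparative waning claim and restate the aim as persistence of antibody above baseline at the post-vaccination draw. Label any association with time since vaccination as between-child and indirect.
3. **Primary analysis.** Confirm the baseline draw in Methods. Name the paired change in Global IgG as primary, reported as geometric mean fold rise with 95% CI. In the linear models, use log post-vaccination Global IgG (or the log ratio) adjusted for log baseline, because fold rise can depend on the starting level.
4. **Responders.** Fix one cut-off, with its source, before assay results are seen, and report the proportion with an exact 95% CI. A formal adequate/suboptimal/inconclusive rule is optional, and its behaviour depends on the assumed bar and n. For example, with n = 100 and adequacy declared only if the lower limit exceeds the bar, a 70% bar needs at least 80 responders. True rates of 80%, 82% and 83% then meet it with probability 56%, 75% and 83%. An 80% bar needs at least 89, and a true rate of 90% meets it with probability 70%.
5. **Sampling window.** The passages giving 6 months (± 4 months) and 4-6 months must be reconciled.

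**Cost.** This takes rewording, one documented cut-off and one paired analysis, with no new samples if the listed baseline draw is taken. Children without a baseline sample leave the paired analysis. The comparative and waning claims are given up; keeping them would need a comparison group or reference and at least one further post-vaccination sample per child.

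### Hypothesis 2 compares waning in T1DM with the general population, but the plan has no comparator, named reference, waning endpoint or waning analysis

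*Combined protocol and SAP*

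**What the plan says.** **The claim.** Under Research Question and Aims, Specific Aim 2 is "To assess if patients with T1DM have waning of immune response to PPSV23 six months following vaccination". The first sentence of its hypothesis is comparative: "Hypothesis 2: T1DM children will have higher waning of immunity as compared to general population without T1DM".

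**Who is studied.** Subject Information gives "Subject population (children, adults, groups): children ages 3-18 years", and the one inclusion criterion listed is "Clinical diagnosis of Type 1 diabetes". Target accrual is 100, with no division into groups.

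**When blood is drawn.** Study Design and Methods states "Vaccine response as assessed by Global IgG will be drawn 6 months after immunization (+/- 4 months", that is, 2 to 10 months, and adds "Blood draws will be aligned when possible with the participant's quarterly clinical hemoglobin A1C checks". Biospecimens section a, a form section for healthy adults, is filled in as "twice: baseline 4-6 months post immunization". Section b, which covers children, has "baseline 4-6 months post immunization" with no count. Methods does not describe a baseline draw; baseline appears only in the Biospecimens entries.

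**What is analysed.** The primary endpoint is serological response by Global IgG. The secondary endpoint is that response by diabetes-control characteristics. The Data Analysis Plan has descriptive statistics and linear models of response on a list of clinical variables that ends in an open-ended etc. Neither section mentions waning, baseline IgG, time since vaccination or a group without T1DM.

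**The concern.** A hypothesis about a difference between two populations needs data on both, or a reference fixed in advance. A hypothesis about waning needs a measure of decline. Here the plan supplies neither, so the first sentence of Hypothesis 2 has no test.

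The practical risk lies in the report. A low IgG level around six months could be described as waning when it may equally reflect a weak initial response. A literature value chosen after the results are known could be used as the general-population comparator. The Background says that the findings may inform the need for booster vaccination. A response that was never mounted and one that was mounted and lost are different findings for that purpose.

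**Working it through.** The plan gives no power calculation, effect size, SD or antibody half-life, so there is no stated figure to reproduce. The first two steps rest on the text alone. The others illustrate scale on assumed inputs.

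**1. The comparison.** A child without T1DM is ineligible, so the planned number of comparators is 0. No historical cohort, published value or external dataset is named as a reference. The controlled and case-control studies in the reference list are cited as background only. The contrast has one side and cannot be estimated until a reference is named.

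**2. Endpoint and analysis.** The listed endpoints and models concern response. They bear on the second sentence of Hypothesis 2 (age, duration, glycemic control), but for response and not for waning.

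**3. Decline within a child.** This step takes the natural reading of one baseline and one post-vaccination draw. Assume level = peak × 2^(−t/half-life), with the peak at vaccination, in fold over baseline.

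| Peak | Half-life | 2 months | 6 months | 10 months |
|---|---|---|---|---|
| 8-fold | 6 months | 6.35 | 8 × 2^(−1) = 4.0 | 2.52 |
| 5.66-fold | 12 months | 5.04 | 5.66 × 2^(−0.5) = 4.0 | 3.17 |
| 4-fold | no decline | 4.0 | 4.0 | 4.0 |

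One value at six months cannot tell these three histories apart.

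**4. Slope on draw time between children.** Inputs: n = 100 and two-sided alpha 0.05 from the plan. Assumed: draw times uniform over the window, residual SD 0.8, 1.2 or 1.6 log2, half-life 6 or 12 months.

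- Slope = 1/half-life in log2 per month.
- SD of draw time = width/√12: 8/√12 = 2.309 months (2–10) and 2/√12 = 0.577 months (4–6).
- Noncentrality = slope × SD of draw time × √n / residual SD, normal approximation. For example, (1/6) × 2.309 × 10 / 0.8 = 4.81, which gives 99.8%.

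| Window | Half-life | SD 0.8 | SD 1.2 | SD 1.6 |
|---|---|---|---|---|
| 2–10 months | 6 months | 99.8% | 89.4% | 67.2% |
| 2–10 months | 12 months | 67.2% | 36.1% | 22.5% |
| 4–6 months | 6 months | 22.5% | 12.6% | 9.2% |
| 4–6 months | 12 months | 9.2% | 6.9% | 6.0% |

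Draw time is not assigned, so even a well-powered slope is open to confounding by whatever determines when a child is seen.

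**5. Leaving draw time out of the models.** If draw time is unrelated to the predictors, the share of effective sample size lost is v/(SD² + v), with v = (SD of draw time / half-life)².

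- 2–10 months, half-life 6: v = (2.309/6)² = 0.148. The loss is 0.148/(0.64 + 0.148) = 18.8% at SD 0.8 and 0.148/(2.56 + 0.148) = 5.5% at SD 1.6.
- 2–10 months, half-life 12: v = 0.037. The loss is 5.5% and 1.4%.
- 4–6 months, half-life 6: v = (0.577/6)² = 0.0093. The loss is 1.4% and 0.4%, and smaller still at half-life 12.

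If draw time is related to A1C, age or another predictor, leaving it out can bias that predictor's coefficient, and this formula does not measure the bias.

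**The case against.** The strongest reply is that one hypothesis sentence is at fault while both listed endpoints stand without it. That is right and limits the severity, but it does not supply the missing test.

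Other replies stand in part:

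- **The healthy-adult blood-draw section is filled in.** A reader might infer a control group. The stated population is children with T1DM, so the entry does not create one.
- **The sponsor may compare with published data.** That is possible, so the comparison is not beyond repair. The reference would have to be named beforehand.
- **The open-ended etc. could include time since vaccination.** It could. The documents leave the term unstated and do not exclude it.
- **The two draw windows may be compatible.** The interval 4–6 months lies inside 2–10 months and could be a target within an allowed range. A reader might call this a flat contradiction, but the text supports only that the two statements differ and need reconciling.
- **The single post-vaccination draw is an interpretation.** This is correct. The entry lacks a separator, possibly lost in reading the PDF, and the section for children gives no count. The comparator and endpoint gaps do not depend on it.
- **The power figures rest on invented inputs.** They are assumptions and show scale only.

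**Conclusion.** The point holds, and it should be fixed. With certainty from the text, the first sentence of Hypothesis 2 cannot be tested as planned: there is no comparator, no named reference, no waning endpoint and no waning analysis. On the natural but not explicit reading of the draw schedule, decline within a child cannot be estimated either.

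A reader might go further and conclude that the study can carry no information about decline. The documents do not support that. Under the wide window and favourable assumptions, a between-child slope could be well powered. But power falls to 22.5% over 2–10 months, and to between 22.5% and 6.0% over 4–6 months, within plausible assumed inputs. The slope is also observational, so it cannot be relied on to show waning.

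Omitting draw time costs about 1.4% to 19% of effective sample size over 2–10 months and at most 1.4% over 4–6 months if it is unrelated to the predictors. It may cause bias if it is related. A reader might also infer that the primary endpoint fails, and nothing here shows that. Whether the overall Hypothesis and Hypothesis 1 have an adequate reference is not assessed.

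**What to change.** 1. **Aim and hypothesis.** Delete the comparison with the general population, or name a specific external reference in advance. Restate Aim 2 as persistence of Global IgG in T1DM at the sampled time, and do not describe a single post-vaccination level as waning.
2. **Endpoint and analysis.** Add a matching secondary endpoint: change in Global IgG (log-transformed if needed) from baseline to the post-vaccination draw, with a 95% confidence interval. Put baseline IgG and months since vaccination into the planned linear models. Report the time coefficient as an exploratory between-child estimate whichever window applies.
3. **Draw schedule.** Reconcile the timing in Methods with that in Biospecimens, and state the number of draws for children.

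With 100 paired values the half-width of the interval for mean change would be 1.96/√100, about 0.20 SD of the change.

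**Cost.** The changes are wording, one endpoint and two model terms, and need no extra children or samples. The Aim 2 claim becomes weaker and largely overlaps Aim 1, because it uses the same sample, assay and covariates. If the sponsor wants to keep waning within T1DM as the aim, at least two post-vaccination samples per child are needed. On the natural reading of the schedule, that is one more research draw each.
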